## 2. Aims

### Primary Aim:

To measure adherence with quality performance indicators (QPIs) for the management of AP during the first 72 hours after admission in AoNZ.

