## 3. Quality Performance Indicators

Multiple practice guidelines have been published for the management of AP (14–19). The recommendations in these guidelines are usually based on a systematic review of the relevant literature and the evidence on which is based on the available evidence, which is usually graded. Quality performance indicators will be drawn from these evidence-based recommendations for each of the nominated management domains that are relevant to the management of patients within the first 72 hours from admission to hospital. Any differences in the recommendations between the source guidelines will be resolved by discussion amongst the Scientific Advisory Group and consensus established for the QPIs.

The QPIs were developed for the following management domains: (Appendix D: Table 1 with guidelines)

**Table 1.** Quality Performance Indicators

	Domain	QPI	Ref*	Metrics
1	Diagnosis	All patients diagnosed within 12 hours of admission	IAP	RAC criteria for diagnosis: enzymes 3xUL, typical pain ± CT scan
2	Aetiology	All patients had tests for aetiology determined within 24 hours of admission	IAP	U/S for gallstones ETOH history with intake (units per week, timing of binge to pain) If both negative then lipids, IgG4, drugs
3	Severity (predicted)	All patients had prediction of severity on admission	IAP	N / Y, if yes method (drop-down of all options and other) Further drop-down bar will the give options for severity (mild, moderate, and severe)

4	Severity (actual)	All patients had actual severity determined at 48 hours	-	N / Y, if yes method (drop-down RAC, DBC and other) Further drop-down bar will the give options for severity (mild, moderate, and severe)
5	CT scan	Initial CT assessment performed after 72-96 hours if poor response to initial management or clinical deterioration, unless there is diagnostic uncertainty. Not required for severity prediction.	IAP	N / Y, if yes indication (drop-down with other)
6	Transfer	All patients with predicted or actual severe AP in the first 72 hours are discussed with specialist pancreas service.	Nice	N / Y Indication for transfer (drop-down)
7	Analgesia	All patients given narcotic analgesia within one hour of admission	-	Step-up or step-down approach? IV analgesia given on admission N / Y NSAIDS given to mild AP Analgesics prescribed

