### 4.2. Secondary outcomes

- Variation in compliance with QPIs between hospitals for each of the management domains
- Requirement for mechanical ventilation (invasive and non-invasive)
- Requirement for renal replacement therapy
- Requirement for inotropic or vasopressor support
- Intervention for a complication of AP
- Alive and discharged at 30-days

[figure not shown]

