Indication for NBM	for ultrasound scan/ for surgery/ for ERCP/ unknown reason/ other (please specify)
Patient tolerating PO oral intake (clear fluids) by 24 hours	Yes/no
Patient tolerating PO oral intake (clear fluids) by 48 hours	Yes/no
Patient tolerating PO oral intake (clear fluids) by 72 hours	Yes/no
Enteral feeding started in the first 72 hours?	Yes/no
Tolerating enteral feed	Yes/no
Type of Enteral feeding	NJ/NG
Rate of enteral feed	ml/hr
PN in the first 72 hours?	Yes/no
Rate of PN	ml/hr
Anticoagulation	
On regular anticoagulation therapy prior to admission	Warfarin/ dabigatran/ rivaroxaban/ other (please specify)/ Not on regular anticoagulation therapy
Regular anticoagulation continued on admission	Yes/No
(If yes) type of anticoagulation drug	warfarin/ dabigatran/ rivaroxaban/ other
Regular anticoagulation commenced on	Yes - at 24 hours/ Yes - at 48 hours/ No

admission	
Anticoagulation commenced on admission	Prophylactic-dose clexane/ treatment-dose clexane/ anticoagulation not started/ other (please specify)
Local complications in the days prior to the 30-day follow-up	
Necrotising pancreatitis ( Appendix B )	Yes/no
Acute necrotic collections (ANC)	Yes/no
Infected ANC	Yes/no
(If yes) intervention	Endoscopic/ percutaneous/ open necrosectomy
(if yes) date of intervention	Date (dd/mm/yyyy)
Acute pancreatic fluid collection (APFC)	Yes/no
Infected APFC	Yes/no
(if yes) intervention	Endoscopic/ percutaneous/ open necrosectomy
(if yes) date of intervention	Date (dd/mm/yyyy)
Portal/ splenic vein thrombosis	Yes/no
Other local complications	Pleuro-peritoneal fistula/ pleural effusion/ enteric fistula/ gastrointestinal bleeding/ pancreatic ascites/ arterial pseudoaneurysm/ other (free text)
Organ failure and other outcomes during the last 30-days follow-up	
Final aetiology	Alcoholic/ gallstone/ hypertriglyceridaemia/ others
Acute renal failure (as per RIFLE criteria - Appendix A )	Yes/no
Acute renal failure > 48 hours	Yes/no
ICU admission	Yes/no
(If yes) duration of ICU admission	day(s)
New renal dialysis required	Yes/no
(If yes) duration of dialysis	day(s)
New high-flow oxygen/ AIRVO requirement	Yes/no
Duration of high-flow/ AIRVO	days
Noninvasive ventilation required	Yes/no
(If yes) duration of noninvasive ventilation	days
Mechanical ventilation required	Yes/no

(If yes) duration of mechanical ventilation	day(s)
Inotropes required	Yes/no
(If yes) duration of inotropic support	day(s)

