## 5.6. Follow-up

All patients will be followed for the initial 72 hours following admission into ED by a clinician and then again chart reviewed at 30 days from initial admission.

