## 8. Statistical analysis

The study will be reported in accordance with the Strengthening the Reporting of Observational Studies in Epidemiology (STROBE) statement (21). The primary analyses will be descriptive assessments of adherence to unambiguous recommendation in the selected domains of early AP management. Descriptive analysis will be performed where normal continuous variables will be compared via student's t test, and non-normal continuous variables will be compared via Mann-Whitney U test; if >2 categories a one-way ANOVA or Kruskal-Wallis test will be used for normal and non-normal variables respectively, Chi-square tests will be used to detect differences between categorical variables. All analyses will be conducted under a two-tailed hypothesis. Multiple imputation may be used in the case of missing data.

Secondary analyses will evaluate the differences in results according to the hospital. Risk-adjusted funnel plots will be produced to test the performance of individual, anonymised centres for normal rates of primary and selected secondary outcomes. Funnel plots' Y-axes will demonstrate QPI of a management domain and X-axis will show the number of patients admitted in each hospital. Furthermore, differences in clinical outcomes between patients that are managed according to best available evidence (QPI) and those that were not will be explored through mixed effects multivariable logistic models. These models will use the patient at the fixed effect level 1 and the hospital as the random effect level 2 (using the R lmer package) will be performed. A one level, fixed effect binary logistic regression model using a pooled dataset from 5 multiply imputed datasets will also be used in the event of substantial missing data.

Variable selection will be based on statistically significant univariable analysis and those variables deemed clinically significant. Fixed, forced entry will be used to adjust the main outcome measure, The effect of interaction, and sequential removal of non-significant variables will be assessed using changes in Akaike information criteria for multilevel models, and p-values for multiple imputed fixed models.

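### Organ support has no start date, so the comparison of outcomes by QPI compliance cannot tell organ failure that preceded late-window QPIs from organ failure that followed them

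*Protocol*

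**What the plan says.** **Exposure.** The primary aim (Section 2) is adherence to QPIs for the "management of AP during the first 72 hours after admission in AoNZ". Table 1 in Section 3 gives each QPI its own window, from one hour to 72 hours or beyond. QPI 5 reads "Initial CT assessment performed after 72-96 hours if poor response to initial management or clinical deterioration", and its only stated exception is diagnostic uncertainty.

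**Outcomes.** Section 4.2 lists organ-support outcomes without any limit on timing, for example "Requirement for inotropic or vasopressor support". Section 5.6 says that patients are "then again chart reviewed at 30 days from initial admission", and the form in Section 5.5 heads this block "Organ failure and other outcomes during the last 30-days follow-up". Nothing sets aside events in the first 72 hours.

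**Timing fields.** Mechanical ventilation is a yes/no item followed by "If yes) duration of mechanical ventilation". Inotropes are a yes/no item followed by "If yes) duration of inotropic support". Dialysis and non-invasive ventilation follow the same pattern, as do ICU admission and high-flow oxygen. Death, discharge and the recorded interventions do carry a date.

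**Analysis.** Section 8 will explore "differences in clinical outcomes between patients that are managed according to best available evidence (QPI) and those that were not" with mixed-effects logistic models, and gives no rule on the order of exposure and outcome. Section 2 adds stratification by AP severity without saying whether predicted or actual severity is meant.

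**The concern.** A comparison of outcomes by compliance is interpretable only if compliance was settled before the outcome began. Here both clocks start at admission, and some QPIs are settled up to three days later. A patient who needs organ support on day 1 may then be scored as compliant or non-compliant partly because of it. The secondary aims that link compliance to clinical outcomes would absorb that effect. Section 1 expects the study to show any excess morbidity that goes with non-compliance, so a distorted association could be read as evidence about care.

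**Working it through.** **1. Which QPIs can be affected (Table 1, Section 3).**

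| QPI | When it is settled | Link to early organ failure |
|---|---|---|
| Analgesia, first fluids | 1 hour | Little |
| Diagnosis | 12 hours | Little |
| Aetiology, anticoagulation | 24 hours | Limited |
| Actual severity | 48 hours | Judged after early organ failure |
| CT | 72-96 hours | As worded, a CT before 72 hours for deterioration is a breach; the form lists deterioration as an indication for such a CT |
| Discussion with specialist service | First 72 hours | Applies only to predicted or actual severe AP |
| Enteral nutrition | 72 hours | Applies only to moderately severe or severe AP |

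In Appendix A, organ failure for more than 48 hours defines severe AP, and shorter organ failure is one route to moderately severe AP. Early organ failure can therefore make a patient eligible for items that a mild case cannot breach.

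**2. Can the order be recovered from the form?** Not for organ support. Four days of ventilation could be days 1 to 4 or days 10 to 13, and the entry would be the same. ICU admission, also recorded only as yes/no and duration, cannot stand in for a date.

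**3. Does severity stratification solve it?** Stratifying by actual severity conditions on organ failure, which overlaps the outcome. Documented predicted severity may be drawn from notes up to 72 hours (Section 5.5), so it can also follow onset.

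**4. How large could the bias be?** The protocol gives no event rate, breach rate or effect size, so there is no figure to reproduce. All inputs below are assumptions: 600 patients, 5% with organ support (30 events), half of them early (E = 15 early, L = 15 late), breach rate b = 40% in everyone without early organ support, and no true effect of compliance. Let q be the breach rate in early-event patients.

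Breaching events = 15q + 15 × 0.40. Non-events = 570, of whom 228 breach and 342 do not.

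OR = [(15q + 6) / (15(1 − q) + 9)] ÷ (228/342)

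| q | Events: breach / no breach | Crude OR |
|---|---|---|
| 30% | 10.5 / 19.5 | 0.81 |
| 40% | 12 / 18 | 1.00 |
| 60% | 15 / 15 | 1.5 |
| 80% | 18 / 12 | 2.25 |

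The number of patients and the event rate cancel out. Only b, q and the early share matter. Varying the early share (9 early and 21 late, or 21 early and 9 late):

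| q | 30% early | 70% early |
|---|---|---|
| 30% | (11.1/18.9) ÷ (228/342) = 0.88 | (9.9/20.1) ÷ (228/342) = 0.74 |
| 60% | (13.8/16.2) ÷ (228/342) = 1.28 | (16.2/13.8) ÷ (228/342) = 1.76 |
| 80% | (15.6/14.4) ÷ (228/342) = 1.63 | (20.4/9.6) ÷ (228/342) = 3.19 |

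**5. Does a landmark remove it?** With half the events early, dropping the 15 early events leaves 15 late events, 6 breaching and 9 not. (6/9) ÷ (228/342) = 1.00, whatever q is. The step needs to know which events were early, and the form does not record that for organ support.

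**The case against.** Much of the case on the other side stands.

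- **Direction.** A reader might infer that the plan will make non-compliance look harmful. The documents do not support that. Sicker patients may get fuller work-up. Early deaths leave less time to breach late items, which pulls one way; early discharge of well patients pulls the other. If early organ support leaves breach rates unchanged, the odds ratio is 1.00.
- **Nil by mouth.** A reader might add that ventilated patients are fasted and so breach QPI 11. That QPI excuses a clear reason, and the form asks only about fasting on admission, so the example fails.
- **Scope.** It would be too broad to say that all compliance accrues to 72 hours or that no outcome can be ordered. Several QPIs close within 1 to 24 hours, and Section 2 plans analyses by domain. Death, discharge and recorded interventions are dated. The indication for early CT is recorded, so those cases can be separated.
- **Crude figures.** The odds ratios above are unadjusted, while Section 8 plans multivariable models. They illustrate the mechanism and do not predict the study's result. Adjustment does not, however, supply the missing order.
- **Role of the SAP.** A landmark rule may properly sit in a SAP, which is not at hand. But no SAP can derive organ-support onset from a duration. Local leads keep a key that would allow a return to the notes, though the protocol does not plan this.
- **Stakes.** Section 8 calls the comparison exploratory, and Section 1 does not rest national standardisation on this model alone.

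**Conclusion.** The point holds in a limited form. Organ-support onset is undated, so its order relative to late-window or deterioration-triggered QPIs cannot be established from the planned data. Stratifying by actual severity does not cure this. The secondary comparison of outcomes by overall compliance, or by those QPIs, is open to bias of unknown direction. With half the events early, the crude odds ratio runs from 0.81 to 2.25 under no true effect; with 30% to 70% early it runs from 0.74 to 3.19. These ranges rest wholly on assumed breach rates and early shares. That organ failure changes compliance is plausible from the wording of the QPIs but is not shown in the protocol. The primary outcome is descriptive and unaffected. The point is worth correcting but does not threaten the study's main result.

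A separate, smaller gap is that Section 4.2 counts any intervention for a complication, while the form has intervention fields only under infected ANC and infected APFC. Other listed complications, such as bleeding or pseudoaneurysm, have none.

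**What to change.** **Section 5.5.** Add a start date and time to dialysis, non-invasive ventilation, mechanical ventilation and inotropes. Add one item for any intervention for a complication, with type, indication and date.

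**Section 8.**
- For models using overall compliance or late-window QPIs, count outcomes after 72 hours among patients alive and free of that outcome at 72 hours. Keep patients discharged earlier. Use the existing dates for death and interventions; these carry no clock time, so state a rule for events on the calendar day when the 72 hours end.
- Report events before 72 hours descriptively.
- As a sensitivity analysis, score every patient on one fixed set of QPIs whose windows close by 24 hours, and count outcomes after 24 hours. The set should be the same for all; scoring each patient only on QPIs that closed before their own event would make exposure depend on outcome timing. Some form items for aetiology and predicted severity accept information up to 72 hours, so those QPIs can join the set only if a 24-hour answer is recorded.
- Describe the results as associations.

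**Cost.** Four start-time entries, one intervention item and a paragraph in Section 8. The 30-day data already come from chart review. If entry has closed, the local key would allow retrieval for the patients who had organ support. The landmark models will have fewer events and wider intervals.

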### Secondary Aims:

- To measure the variation in compliance with QPIs between each hospital in AoNZ for each management domain for the management of AP during the first 72 hours after admission.
- To correlate compliance (overall and for each management domain) with QPIs and defined clinical outcomes stratified by AP severity.
- To compare clinical outcomes between compliant and non-compliant management of patients stratified by AP severity.

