All hospital leads will also be required to complete a hospital-survey which assess hospital-related variables (*Appendix C*).

Data collection will occur at two timepoints. The first time point will be within or at 48 hours of admission to hospital and secondly at 30-days follow-up following admission to the emergency department .

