**Appendix C - Hospital Survey**

Questions	Options
How many beds does your hospital have?	
How many ICU beds does your hospital have?	
Does your hospital have a high dependency unit (HDU)?	Yes/no
(If yes) how many beds does your HDU have	value
Do you have an interventional radiology service at your hospital?	Yes/no
Do you have an endoscopy service at your hospital?	Yes/no
Is ERCP routinely offered to patients in your hospital?	Yes/no
Is EUS routinely offered to patients in your hospital?	Yes/no

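### The Section 8 outcome model does not separate within- from between-hospital compliance, so the compliance odds ratio can absorb hospital differences if hospital outcome effects correlate with hospital compliance

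*Protocol*

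**What the plan says.** Section 8 names as its subject "differences in clinical outcomes between patients that are managed according to best available evidence (QPI) and those that were not". The method follows in the same sentence: these contrasts "will be explored through mixed effects multivariable logistic models". On structure it says: "These models will use the patient at the fixed effect level 1 and the hospital as the random effect level 2". The natural reading is a random intercept for hospital, although the protocol does not use that term. No hospital-mean compliance term, within/between split or hospital fixed effect is named.

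The covariates are left open: "Variable selection will be based on statistically significant univariable analysis and those variables deemed clinically significant". If much data is missing, Section 8 also calls for a single-level logistic model on five multiply imputed datasets. That model has no hospital term.

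The protocol treats hospital differences in compliance as a target in their own right. A secondary aim in Section 2 is "To measure the variation in compliance with QPIs between each hospital in AoNZ for each management domain", and the first secondary outcome in Section 4.2 is "Variation in compliance with QPIs between hospitals for each of the management domains". Under Section 5.3 each hospital lead must "complete a hospital-survey which assess hospital-related variables". Appendix C lists the items, starting with bed numbers (for example "How many ICU beds does your hospital have") and going on to HDU, interventional radiology, endoscopy, ERCP and EUS. Section 8 neither gives these items a role nor rules them out.

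**The concern.** A random-intercept model estimates the patient-level compliance association without bias only if the hospital intercepts are independent of compliance. Otherwise the single compliance coefficient blends two contrasts: compliant against non-compliant patients in the same hospital, and hospitals of high against hospitals of low compliance.

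The protocol's own definitions offer a route to dependence. Some indicators rest on local resources: the ERCP indicator in Table 1 is one, and Appendix C asks whether ERCP is routinely offered. Most of the secondary clinical outcomes are treatments received (ventilation, renal replacement, vasopressors, intervention for a complication), and these can depend on ICU, HDU and interventional radiology capacity. One hospital characteristic could therefore influence both exposure and outcome.

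Section 1 says the study will show any excess morbidity that goes with non-compliance, and that the data can be used to standardise care nationally. An odds ratio that partly compares different kinds of hospital does not answer that question cleanly. The primary, descriptive analysis is not affected.

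**Working it through.** The protocol gives no sample size, alpha or effect size for this model, so there is no stated figure to reproduce. The check is by simulation with the true within-hospital odds ratio set to 1.

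**Size of the data.** Incidence is 58 per 100,000 adults per year (Section 1) and enrolment lasts 3 months (Study Summary). The adult population is assumed to be 4.0 million: 58/100,000 × 4,000,000 ÷ 4 = 580 patients (508 to 624 for 3.5 to 4.3 million). The number of hospitals is also assumed: 580 ÷ 20 = 29 per hospital, or about 24 each in 24 hospitals (576).

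**Other assumptions.** Hospital sizes are unequal; mean compliance is about 50%; hospital effects are normal on the logit scale; there are no patient covariates; the test is two-sided at 5%.

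**Layout A.** 20 hospitals averaging 29 patients, compliance SD 1.0, 1,000 runs per row. Entries are median odds ratio and false-positive rate. The one-level model was fitted to complete data.

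| Outcome rate | Outcome SD | Correlation | One-level | Random intercept | Random intercept + hospital mean |
|---|---|---|---|---|---|
| 10% | 0.5 | 0 | 1.02, 6.6% | 1.01, 4.6% | 1.01, 4.9% |
| 10% | 0.5 | -0.5 | 0.84, 13.4% | 0.89, 7.2% | 1.01, 5.8% |
| 10% | 0.5 | -0.8 | 0.74, 21.7% | 0.82, 10.2% | 1.00, 4.2% |
| 20% | 0.8 | -0.8 | 0.64, 56.8% | 0.87, 10.2% | 1.01, 5.4% |

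**Layout B.** 24 hospitals averaging about 24 patients, 10% outcome, compliance SD 0.8, outcome SD 0.5, 600 runs, random-intercept model.

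| Correlation | Odds ratio | False positives |
|---|---|---|
| 0 | 1.00 | 4.5% |
| 0.3 | 1.07 | 4.5% |
| 0.5 | 1.12 | 5.0% |
| 1.0 | 1.25 | 10.8% |

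With SDs of 0.5 and 0.4 the results are 1.07 and 4.3% at correlation 0.5, and 1.13 and 7.0% at 1.0. A separate run with 24 hospitals of about 24 patients gave 1.11 and 5.8% at correlation 0.5, and 1.26 and 11.8% at 1.0. With the hospital mean added, that run gave odds ratios of 0.98-1.02, false-positive rates of 4-6% and standard errors 3-5% wider.

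The sign of the correlation sets only the direction of the shift. The Monte Carlo standard error of a rejection rate is 0.7 to 1.6 points at 1,000 runs; near 5% with 600 runs it is √(0.05 × 0.95 ÷ 600) = 0.9 points.

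**Why hospital size matters.** As an approximation, the random intercept recovers a share λ = σ²np(1−p) ÷ [1 + σ²np(1−p)] of a hospital's effect, where σ is the outcome SD, n the patients per hospital and p the outcome rate.

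- σ = 0.5, n = 29, p = 0.10: 0.25 × 29 × 0.09 = 0.65, so λ = 0.65 ÷ 1.65 = 0.39. About 61% of the one-level bias should remain. Simulated: ln 0.82 ÷ ln 0.74 = 0.66.
- σ = 0.8, n = 29, p = 0.20: 0.64 × 29 × 0.16 = 2.97, so λ = 2.97 ÷ 3.97 = 0.75. About 25% should remain. Simulated: ln 0.87 ÷ ln 0.64 = 0.31.
- σ = 0.5, n = 1,000, p = 0.10: 0.25 × 1,000 × 0.09 = 22.5, so λ = 22.5 ÷ 23.5 = 0.96. Almost nothing should remain. Simulated odds ratio 0.98 (200 runs).

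The leak is therefore a feature of small hospitals, which is the setting that three months of enrolment implies.

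**The case against.** A hospital random effect is a standard choice, and nothing in Section 8 is false. Four objections carry weight.

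- **Variation is not correlation.** A reader might infer that the protocol contradicts the model's assumption because it expects compliance to differ between hospitals. It does not. With large compliance variation and zero correlation there is no bias, and the documents give no evidence of a correlation. The capability argument makes one plausible and no more.
- **A false link is not inevitable.** A reader might infer that the planned odds ratio will be spurious. At a correlation of 0.5 the false-positive rate stays near nominal (5.0% to 7.2%). The 10-12% figures need correlations of 0.8 to 1.0, and no covariates were simulated.
- **Hospital is not handled only through the random effect.** The covariate rule in Section 8 is open and could admit survey items, and a statistical analysis plan, not shown here, may add terms. This stands, so the claim cannot be that hospital characteristics are excluded. But survey items would remove only the measured hospital differences, whereas a hospital-mean term protects the within-hospital contrast whatever the cause.
- **Patient-level confounding remains.** Several indicators in Table 1 apply only to patients with severe or predicted severe disease, or with cholangitis. A within-hospital odds ratio is not a causal compliance effect either, and Section 8 promises only to explore differences.

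The objection that this is merely detail for an analysis plan does not stand. The protocol itself fixes the model form, and a better form is available from data already collected.

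**Conclusion.** The point holds conditionally. As written, the outcome model can mix within- and between-hospital associations, and whether it does so depends on a correlation that the documents neither show nor exclude. At a 10% outcome rate and the assumed hospital sizes, the shift from a true odds ratio of 1 is nil at zero correlation. It is about 1.1 (or 0.9) with roughly 5-7% false positives at 0.5, and about 1.2-1.3 (or 0.8) with about 10-12% at 0.8 to 1.0. The number of hospitals, the adult population, the SDs and the correlations are all assumptions.

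The one-level model for imputed data is more exposed because nothing in it absorbs hospital differences. In the three correlated rows of layout A its odds ratio was 0.84, 0.74 and 0.64, with false-positive rates of 13.4%, 21.7% and 56.8%. The point concerns a secondary analysis, but it is the one that supports statements about morbidity and non-compliance.

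**What to change.** In Section 8:

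- Enter compliance as two terms, the patient's own compliance and the mean compliance of that patient's hospital, and keep the hospital random intercept. Compute the mean separately for each compliance measure (overall and by domain), over the patients in that model.
- Report the within-hospital odds ratio as the patient-level compliance association, stating that it remains open to confounding by patient severity. Report the hospital-mean coefficient separately, and name the Appendix C variables as eligible hospital-level covariates.
- Put the same hospital-mean term and a hospital effect into the model for the imputed data, so that it no longer drops hospital.

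The cost is a few sentences, one derived covariate per compliance measure, and standard errors about 2-5% wider. No new data are needed.

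### The added imputed outcome model omits the hospital level and uses a different removal rule, so it cannot show the effect of missing data, and its standard errors can be too small

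*Protocol*

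**What the plan says.** All of this is in Protocol Section 8 (Statistical analysis). Differences in clinical outcomes between patients managed according to the quality indicators and those not "will be explored through mixed effects multivariable logistic models". On structure it says: "These models will use the patient at the fixed effect level 1 and the hospital as the random effect level 2". The software is named in brackets after this: "using the R lmer package".

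A second model follows: "A one level, fixed effect binary logistic regression model using a pooled dataset from 5 multiply imputed datasets", which "will also be used in the event of substantial missing data". No hospital term or cluster-robust variance is given for it. Earlier in the section, multiple imputation is mentioned only as an option.

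On covariates, "Variable selection will be based on statistically significant univariable analysis", and the same sentence also admits variables judged clinically significant. The next sentence speaks of fixed, forced entry, and then of interactions and stepwise removal, judged by changes in AIC for the multilevel models and by "p-values for multiple imputed fixed models".

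Section 4.2 lists between-hospital variation in compliance as a secondary outcome. Compliance is the exposure in these models.

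**The concern.** An analysis with imputation is normally set beside the main analysis to show whether missing data matter. That works only if everything else is held fixed. Here the imputed model also loses the hospital level and may end with other covariates. When missing data are substantial, the team would hold one model that handles hospital and one that handles missingness, with no clean way to compare them.

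The second issue is precision. If both compliance and outcome vary by hospital, a one-level model treats correlated patients as independent. The phrase about a pooled dataset also describes pooling data, whereas valid multiple imputation pools estimates. Analysing five completed copies as one file would count every patient five times.

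At stake are the secondary aims in Section 2 that relate compliance to outcomes, and with them the Section 1 rationale of showing excess morbidity from non-compliance.

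**Working it through.** The protocol gives no sample size, number of hospitals, ICC, event rate or significance level, so there is no figure to reproduce. The sizes below rest on assumptions: 20 hospitals, about 29–30 patients each, two-sided 5% tests and the event risks stated. As a plausibility check on size, the Section 1 incidence of 58 per 100,000 per year over three months, with an assumed adult population of 3.5 to 4.5 million, gives 0.00058 × 3.5 million × 0.25 ≈ 508 to 0.00058 × 4.5 million × 0.25 ≈ 652 patients; 20 × 29 = 580 lies between.

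**1. The two models side by side**

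| Feature | Main model | Added model |
|---|---|---|
| Hospital | random effect | no term stated |
| Missing data | not stated to be imputed | "5 multiply imputed datasets" |
| Removal of variables | change in AIC | p-values |
| Odds ratio estimated | conditional on hospital | averaged over hospitals |

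The rows differ together. Even with complete data the two odds ratios need not agree, because they are different quantities and may be adjusted for different variables.

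**2. Ignoring hospital, without stacking**

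Simulation under no effect: 20 hospitals, mean size about 29, event risk 10%, 1,500 runs per setting, one-level logistic model. Outcome ICC = σ²/(σ² + 3.29), with hospital variance σ² = 0.1, 0.36 or 0.8. The exposure's hospital variance on the logit scale was 0, 0.36 or 1.5.

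| Outcome ICC | Exposure variance | Model SE / empirical SD | Type I error |
|---|---|---|---|
| 0.03 | 0 / 0.36 / 1.5 | 1.00 / 0.99 / 0.97 | 4.6% / 4.9% / 5.3% |
| 0.10 | 0 / 0.36 / 1.5 | 0.97 / 0.94 / 0.91 | 5.2% / 5.8% / 7.6% |
| 0.20 | 0 / 0.36 / 1.5 | 1.03 / 0.90 / 0.78 | 4.1% / 8.0% / 11.9% |

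Simulation error near 5% is √(0.05 × 0.95/1500) ≈ 0.6 percentage points. Where the exposure does not vary by hospital there is essentially no loss. The worst setting understates the standard error by about 22%.

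**3. Stacking five copies versus combining estimates**

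Let λ be the share of the estimate's variance that is due to missingness. The ratio of stacked SE to Rubin SE is √((1 − λ)/5), and the actual type I error is 2 × [1 − Φ(1.96 × ratio)].

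| λ | SE ratio | Type I error |
|---|---|---|
| 0 | 0.447 | 38.1% |
| 0.1 | 0.424 | 40.6% |
| 0.3 | 0.374 | 46.3% |
| 0.5 | 0.316 | 53.5% |

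A simulation agrees (580 patients, exposure missing at random in 10%, 20% or 40%, with and without moderate hospital clustering, 600 runs, one-level fits). Stacked SEs were 0.113–0.118 against an empirical SD of 0.274–0.364, with type I error 42–50%. With Rubin's rules the SEs were 0.268–0.352 and the type I error 4–7%. A multilevel imputed model was not simulated.

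**4. Covariates**

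Few events limit how many covariates can be forced in. For illustration, 600 patients with 5% events give 30 events. Entering age (1 parameter), sex (2), ethnicity (5), Charlson index (1), final aetiology (3) and severity (2), as categorised in Section 5.5, takes 14 parameters. With the exposure that is 15, so 30/15 = 2 events per parameter.

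**The case against.** The other side has several good points.

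- A reader might infer that the one-level model replaces the main model when data are missing. The text says it will *also* be used, so it is an addition. This stands. It does not restore comparability, and the AIC/p-value contrast between multilevel and imputed models suggests that the multilevel model is run without imputation.
- A reader might infer that stacking is planned. The phrase may be loose wording for pooling estimates, and nothing says that copies are analysed as independent rows. This stands, so the 38–54% is conditional on the literal reading.
- A reader might cite the design effect 1 + 29 × 0.05 = 2.45 (SE ratio 1/√2.45 = 0.64, type I error about 21%) as the size of the clustering problem. It applies to covariates that are constant within a hospital, such as those in the Appendix C survey. The exposure here is at patient level, and the protocol does not say that survey variables enter the model.
- A reader might infer that univariable screening loses most real confounders: with 600 patients, 30 events and a 40% prevalent factor, screening keeps an odds ratio of 1.5 only about 18% of the time. That ignores the second route of entry on clinical grounds. Nor are forced entry and stepwise removal flatly contradictory, since they could apply to different variables. The sentences are unclear rather than impossible.
- lmer fits linear mixed models, but the text says logistic. This is a slip in a software name, not evidence that the wrong model is intended.
- A random intercept removes only part of any between-hospital confounding, so restoring it should not be presented as a cure for that.

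Combination rules and covariate lists are often left to an analysis plan. Here, however, the protocol itself fixes a one-level model and two different removal rules, and that is open to criticism as written.

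**Conclusion.** The point holds in a limited form. Section 8 specifies an additional imputed model that omits the hospital random effect and applies another removal rule. Its disagreement or agreement with the main model therefore says little about missing data, and no planned model clearly deals with both clustering and missingness. This part follows from the text and needs no assumptions.

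That standard errors are too small is a possibility, not a certainty. For a patient-level exposure the cost of ignoring hospital runs from nothing to moderate under the assumed hospital numbers and ICCs. The severe error depends wholly on the stacked reading, and disappears under Rubin's rules.

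The reach is confined to the secondary compliance–outcome analyses, which the protocol describes as exploratory. The primary outcome in Section 4.1 is a compliance proportion and does not depend on these models.

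**What to change.** Replace the sentence on the one-level model with:

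> Where missing data are substantial, the same mixed-effects logistic model (random intercept for hospital, fitted with a logistic mixed-model routine such as glmer) is fitted in each imputed dataset, with hospital included in the imputation model, and the estimates are combined by Rubin's rules.

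Correct the lmer reference in the same way. Use one covariate set in both models, chosen in advance on clinical grounds and kept short relative to the expected number of events. Drop the univariable-significance screen and the separate AIC and p-value removal rules.

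Choose covariates from what Section 5.5 collects. It records predicted severity as documented in the notes and the method used, but not the physiological inputs for computing a score, so a computed admission severity is not available without new data fields. The Charlson index in Appendix E already scores age, so entering both needs thought.

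The cost is wording in Section 8, a little computing time and possibly wider intervals. No new data are needed.
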